## 13.5. Reporting of Serious Adverse Events and Adverse Events

### 13.5.1. Reporting of Serious Adverse Events to DAIT/NIAID

This section describes the responsibilities of the site investigator to report serious adverse events to DAIT/NIAID and the SACCC via the SAE eCRF. Timely reporting of adverse events is required by 21 CFR and ICH E6 guidelines.

Site investigators will report all serious adverse events (see [Section 13.2.4 Serious Adverse Event \(SAE\)](#)), regardless of relationship or expectedness within 24 hours of discovering the event.

For serious adverse events, all requested information on the AE/SAE eCRF will be provided. However, unavailable details of the event will not delay submission of the known information. Initial SAE eCRFs should include as much information as possible, but at a minimum must include the following:

- AE term
- Relationship to study vaccination (or placebo)
- Relationship to study procedure
- Reason why the event is serious
- Supplementary eCRF pages that are current at the time of the SAE reporting: medical history, concomitant medications, demographics, vaccine/placebo administration

As additional details become available, the AE/SAE eCRF will be updated and submitted. Every time the SAE eCRF is submitted, it should be electronically signed by the investigator or sub-investigator.

For additional information regarding SAE reporting, contact Rho Product Safety:

### 13.5.2. Reporting to Health Authority

After an adverse event requiring 24-hour reporting (per [Section 13.5.1 Reporting of Serious Adverse Events to DAIT/NIAID](#)) is submitted by the site investigator and assessed by the DAIT/NIAID Medical Monitor, there are two options for DAIT/NIAID to report the adverse event to the appropriate health authorities:

#### 13.5.2.1. Annual Reporting

Per 21 CFR 312.33, DAIT/NIAID will include in the Investigational New Drug (IND) Annual Report to FDA all adverse events classified as:

- Serious, expected, suspected adverse reactions (see [Section 13.2.1.1 Suspected Adverse Reaction \(SAR\)](#) and [Section 13.2.3 Unexpected Adverse Event](#)).
- Serious and not a suspected adverse reaction (see [Section 13.2.1.1 Suspected Adverse Reaction \(SAR\)](#)).
- Pregnancies.

Note that all adverse events (not just those requiring 24-hour reporting) will be reported in the IND Annual Report.

#### 13.5.2.2. Expedited Safety Reporting

This option, with 2 possible categories, applies if the adverse event is classified as one of the following:

**Category 1: Serious and unexpected suspected adverse reaction [SUSAR] (see [Section 13.2.1.1 Suspected Adverse Reaction \(SAR\)](#), [Section 13.2.3 Unexpected Adverse Event](#), [Section 13.4 Serious Adverse Event \(SAE\)](#), and 21 CFR 312.32(c)(1)i)).**

The sponsor shall report any suspected adverse reaction that is both serious and unexpected.

The sponsor shall report an adverse event as a suspected adverse reaction only if there is evidence to suggest a causal relationship between the study drug and the adverse event, such as:

1. A single occurrence of an event that is uncommon and known to be strongly associated with vaccine exposure (e.g., angioedema, Stevens-Johnson Syndrome, Guillain-Barré syndrome);
2. One or more occurrences of an event that is not commonly associated with vaccine exposure, but is otherwise uncommon in the population exposed to the drug (e.g., tendon rupture);
3. An aggregate analysis of specific events observed in a clinical trial (such as known consequences of the underlying disease or condition under investigation or other events that commonly occur in the study population independent of treatment) that indicates those events occur more frequently in the treatment group than in a concurrent or historical control group.

**Category 2: Any findings from studies that suggests a significant human risk**

The sponsor shall report any findings from other epidemiological studies, analyses of adverse events within the current study or pooled analysis across clinical studies or animal or *in vitro* testing (e.g. mutagenicity, teratogenicity, carcinogenicity) that suggest a significant risk in humans exposed to the drug that would result in a safety-related change in the protocol, informed consent, investigator brochure or package insert or other aspects of the overall conduct of the study.

DAIT/NIAID shall notify the FDA and all participating investigators of expedited Safety Reports within 15 calendar days; unexpected fatal or immediately life-threatening suspected adverse reaction(s) shall be reported as soon as possible or within 7 calendar days.

**13.5.3. Mandatory reporting to Vaccine Adverse Event Reporting System**

Per the FDA EUA for the Pfizer-BioNTech COVID-19 Vaccine and the FDA EUA for the Moderna COVID-19 Vaccine, the site investigator, or designee, is responsible for mandatory reporting of the following to the Vaccine Adverse Event Reporting System (VAERS):[9, 13]

- vaccine administration errors whether or not associated with an adverse event,
- serious adverse events (irrespective of attribution to vaccination),
- cases of Multisystem Inflammatory Syndrome in adults, and
- cases of COVID-19 that result in hospitalization or death.

The site investigator, or designee, is also responsible for recording vaccination information in the state/local jurisdiction's Immunization Surveillance System or other designated system.

**13.5.4. Reporting of Adverse Events to IRBs/IECs**

All investigators shall report adverse events, including expedited reports, in a timely fashion to their respective IRBs and central IRB in accordance with applicable regulations and guidelines. All safety reports to the FDA shall be distributed by the Sponsor (DAIT/NIAID) or designee to all participating institutions for site IRB submission.

**13.6. Pregnancy Reporting**

The investigator shall be informed immediately of any pregnancy in a study participant. Vaccinations may be discontinued for the pregnant participant after consultation with the site investigator. The investigator shall counsel the participant and discuss the risks of continuing with the pregnancy and the possible effects on the fetus. Monitoring of the pregnant participant shall continue until the conclusion of the pregnancy.

The investigator shall report to the SACCC all pregnancies within 1 business day of becoming aware of the event using the Pregnancy eCRF. The SACCC will report all pregnancies to DAIT/NIAID. All pregnancies identified during the study shall be followed to conclusion, and the outcome of each must be reported. The Pregnancy eCRF shall be updated and submitted to the SACCC, when details about the outcome are available.

Information requested about the delivery shall include:

- Gestational age at delivery
- Birth weight, length, and head circumference
- Gender

- Appearance, pulse, grimace, activity, and respiration (APGAR) score at 1 minute, 5 minutes, and 24 hours after birth, if available
- Any abnormalities.

Should pregnancy complications result in a congenital abnormality, birth defect, miscarriage, or medically indicated abortion – an SAE must be submitted to the SACC, using the SAE reporting procedures described above.

### **13.7. Reporting of Other Safety Information**

An investigator shall promptly notify their local and central IRB, in accordance with applicable regulations and guidelines, as well as the SACC and DAIT/NIAID via email when an “unanticipated problem involving risks to participants or others” is identified, which is not otherwise reportable as an adverse event.

## **13.8. Review of Safety Information**

### **13.8.1. Medical Monitor Review**

The DAIT/NIAID Medical Monitor shall receive reports (approximately every two weeks) from the SACC compiling new and accumulating information on AEs, SAEs, and pregnancies recorded by the study site(s) on appropriate eCRFs.

In addition, the DAIT/NIAID Medical Monitor shall review and make decisions on the disposition of the SAE and pregnancy reports received by the SACC (See [Section 13.5.1 Reporting of Serious Adverse Events to DAIT/NIAID](#) and [Section 12.6 Pregnancy Reporting](#)).

### **13.8.2. DSMB Review**

#### **13.8.2.1. Planned DSMB Reviews**

The NIAID Allergy and Asthma Data and Safety Monitoring Board (DSMB) shall review unblinded outcome and safety data after approximately every 500 participants complete their vaccination schedule. Unblinded data for the planned safety reviews will include, at a minimum, a listing of all reported AEs and SAEs by vaccine arm/placebo and population. Outcome data will show the counts, proportions (with corresponding 95% CI), and difference in proportions between the HA/MCD and comparison group within each vaccine (with corresponding 95% CI) of the primary and key secondary endpoints. Interim p-values will be available upon request. Data may be reviewed and discussed via email or by teleconference. The DSMB may recommend continuing the study, modifying the study, stopping the study, and/or announcing information will the study is still ongoing.

The DSMB will also review results of the planned interim analysis of the primary endpoint (Refer to [Section 14.5.1 Interim Analysis of Primary Endpoint](#)). In addition to reviewing interim analysis results, the DSMB will be asked to consider the nature and severity of the reactions, the rate of reactions in the placebo arm, and the adequacy of information obtained that will allow in-depth characterization of the risk and nature of systemic allergic reactions in the HA/MCD population. The DSMB may recommend continuing the study, modifying the study, or stopping the study. DAIT/NIAID, as sponsor, will determine whether any changes to study conduct will be implemented.

#### **13.8.2.2. *Ad hoc* DSMB Safety Reviews**

In addition to the pre-scheduled data reviews and planned safety monitoring, the DSMB may be called upon for *ad hoc* reviews. The DSMB will review any event that potentially impacts safety at the request

of the protocol chair or DAIT/NIAID Medical Monitor. The DAIT/NIAID Medical Monitor will inform the DSMB of an Expedited Safety Report within 24-48 hours.

In addition, an *ad hoc* comprehensive DSMB Safety Review will be triggered in the event that a study stopping rule is met ([Section 12.5 Study Stopping Rules](#)).

After review of the unblinded data, the DSMB will make recommendations regarding study conduct, including modifications and/or continuation. The DSMB will recommend and DAIT/NIAID, as Sponsor, will determine whether protocol changes should be implemented and/or whether and when enrollment and vaccinations can resume.

#### **13.8.2.2.1. Temporary Suspension of Enrollment and Vaccinations for *ad hoc* DSMB Safety Review**

A temporary halt in enrollment will be implemented by the Sponsor if an *ad hoc* DSMB safety review is required. New participants will not be consented for study participation during the enrollment halt. All vaccinations will be placed on hold. Participants screened but not yet randomized will not be allowed to continue with the Enrollment Visit. All participants not randomized within 7 days of screening must be rescreened.

### **14. Statistical Considerations and Analytical Plan**

#### **14.1. Overview**

The primary research question of this study is to assess the proportion of participants who experience a systemic allergic reaction to either dose of the Pfizer-BioNTech COVID-19 Vaccine, and, independently, of Moderna COVID-19 Vaccine in HA/MCD and comparison populations. This objective will be addressed using a multi-center, randomized, initially-blinded (to the first injection), phase 2 trial in these two populations.

For adults, if no systemic allergic reactions are observed, the within vaccine sample size will be sufficient to rule out a rate as high as 1/275 in the HA/MCD population. If systemic allergic reactions are observed, the within vaccine sample size of 1700 participants was determined to detect a minimum proportion difference between these two populations of ~0.01 with at least 80% power. This translates to a true proportion of 1/100 vs. 1/10,000 in the HA/MCD and comparison populations, respectively.

For children, if no systemic allergic reactions are observed, the within vaccine sample size will be sufficient to rule out a rate as high as 1/50 in the HA/MCD population. If systemic allergic reactions are observed, the within vaccine sample size of 300 participants will detect a minimum proportion difference between the HA/MCD and comparison populations of ~0.05 with approximately 80% power. This translates to a true proportion of 1/20 vs. 1/10,000 in the HA/MCD and comparison populations, respectively.

#### **14.2. Endpoints/Outcomes**

The two primary endpoints are:

1. The proportion of participants who experience a systemic allergic reaction (CoFAR Grade 2 and above regardless of tryptase, or CoFAR Grade 1 with elevated tryptase [1.2 x baseline plus 2 ng/ml]) within the 90-minute post-vaccination observation period to either dose\* of the Pfizer-BioNTech COVID-19 Vaccine

2. The proportion of participants who experience a systemic allergic reaction (CoFAR Grade 2 and above regardless of tryptase, or CoFAR Grade 1 with elevated tryptase [ $1.2 \times$  baseline plus 2 ng/ml]) within the 90-minute post-vaccination observation period to either dose\* of the Moderna COVID-19 Vaccine

\*A participant can have a reaction to either dose 1 or dose 2 (but not to both doses since a participant who has a reaction meeting qualifying criteria to dose 1 will not be able to receive the second dose) or to neither dose.

#### 14.3. Measures to Minimize Bias

To minimize bias, a randomization schedule will be generated by the SACCC and implemented in a validated system that will be used by site personnel to automate the random assignment. For protocol versions 1.0 - 4.0, participants were randomized 2:2:1:1 to receive either the Pfizer-BioNTech COVID-19 Vaccine, Moderna COVID-19 Vaccine, placebo + Pfizer-BioNTech COVID-19 Vaccine, or placebo + Moderna COVID-19 Vaccine. For protocol versions 5.0 – 8.0, participants will be randomized 2:1 to receive active vaccine alone or placebo + active vaccine. The Pfizer-BioNTech COVID-19 Vaccine will be the active vaccine distributed initially.

The randomization scheme will be reviewed and approved by a statistician at the SACCC and will not be modified thereafter except to accommodate any changes required by amendments to the protocol. Furthermore, all first doses of active and placebo vaccine will be blinded to the participant, and all site staff except the unblinded pharmacist and any unblinded personnel administering vaccine and/or scheduling visits. All laboratory assays will be performed by laboratory technicians who do not know the participants' group assignments.

#### 14.4. Analysis Plan

##### 14.4.1. Analysis Populations.

As-treated sample: All participants who are randomized and receive at least one active vaccination. Participants will be analyzed according to the vaccine they received.

Per-Protocol sample: All participants who are randomized and receive all assigned vaccination doses.

Participants who do not receive a second active vaccination due to experiencing an allergic reaction will be included in the analysis. Participants will be analyzed according to the vaccine they received.

Safety sample: All participants who consent and undergo screening procedures. Participants will be analyzed according to the vaccine they actually received, regardless of the treatment arm to which they were randomized. Non-treatment emergent adverse events (e.g., any adverse event that occurs before the first injection) will be summarized in all participants in the safety sample, while treatment-emergent adverse events (e.g., any adverse event that occurs on or after the first injection) will be summarized in the subset of participants who receive any injection (placebo or active).

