### **12.4. Follow-up After Early Study Withdrawal**

Participants who prematurely withdraw (without withdrawing consent) or who are withdrawn may be asked to complete a final phone visit to assess any AEs and concomitant medications as applicable depending on when they are withdrawn relative to the visit schedule. This visit will occur 7 days after the participant received their last vaccine dose. Participants who are withdrawn due to early vaccine termination will be asked to complete study procedures as noted in [Section 6.5 Premature Discontinuation of Investigational Agent](#) prior to being withdrawn from the study. Participants who are withdrawn from the study prior to receipt of study treatment will not be followed after their last completed study visit. Monitoring of a pregnant participant will continue until the conclusion of the pregnancy.

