4. ANALYSIS SAMPLES

As-treated sample: All participants who are randomized and receive at least one active vaccination for any active injection analysis or all participants who are randomized and receive a placebo for any placebo injection analysis. Participants will be analyzed according to the vaccine they received.

Per-Protocol sample: All participants who are randomized and receive all assigned vaccination doses. Participants who do not receive a second active vaccination due to experiencing an allergic reaction will be included in the analysis. Participants will be analyzed according to the vaccine they received.

Safety sample: All participants who consent and undergo screening procedures. Participants will be analyzed according to the vaccine they actually received, regardless of the treatment arm to which they were randomized. Non-treatment emergent adverse events (e.g., any adverse event that occurs before the first injection) will be summarized in all participants in the safety sample, while treatment-emergent adverse events (e.g., any adverse event that occurs on or after the first injection) will be summarized in the subset of participants who receive an injection (placebo or active vaccination).

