8.2. Adverse Events

All AEs will be classified by system organ class (SOC) and preferred term, according to a standardized thesaurus (Medical Dictionary for Regulatory Activities [MedDRA] version 24.0). The severity of non-allergic AEs will be classified using the FDA Guidance for Industry Toxicity Grading Scale for Healthy Adult and Adolescent Volunteers Enrolled in Preventive Vaccine Clinical Trials (September 2007), and the severity of systemic allergic reactions will be graded using CoFAR Grading Scale for Systemic Allergic Reactions Version 3.0. Each AE is entered on the electronic case report form (eCRF) once at the highest severity. As such, no additional data manipulation is needed to identify events.

An overall summary table will be developed to report the number of events and the number and percentage of participants having at least one event in the following categories:

- AEs
- AEs indicated as systemic allergic reactions

- AEs that lead to study treatment discontinuation
- AEs indicated as serious
- AEs with an outcome of death
- AEs that were reported as being related to vaccine/placebo
- AEs reported by severity

In addition, AEs classified by MedDRA SOC and preferred term will be summarized for each treatment group and overall.

Summary tables will present the total number of events as well as the number and percentage of participants experiencing the events. If a participant experiences the same AE on multiple occasions, the event will be counted once for each occurrence when reporting the number of AEs. When reporting the number of participants experiencing the events, a participant will only be counted once if they experience an event within the particular SOC or preferred term.

Percentages will be based on the number of participants in the safety population.

In addition, treatment-emergent AEs classified by MedDRA SOC and preferred term will be summarized for each treatment group, cohort assignment (HA/MCD or Comparison), and overall. The proportion of participants in each study arm experiencing each type of AE will be compared using a Fisher's Exact test. The frequency of treatment-emergent AEs will also be summarized by SOC and preferred term for severity (grade) and relationship to study treatment.

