9. OTHER ANALYSES

9.1. Use of Medications

Medications will be coded according to the World Health Organization (WHO) Drug Dictionary (version 2021-MAR). Medications reported on the CRF will be categorized for analysis as prior, concomitant, or after study treatment by comparing the medication start and stop dates with the first and last dose of study treatment dates. Prior medications will have both the medication start and stop dates prior to the first dose of study treatment date. After medications will have both the medication start and stop dates after the last dose of study treatment date. All other medications will be classified as concomitant, indicating that use of the medication overlapped with use of the study treatment by at least one day.

The number and percentage of participants receiving prior, concomitant, and after medications will be presented overall and by medication class. When reporting the number of participants receiving the medication, a participant will only be counted once if they ever received the medication within the medication class. Percentages will be based on the number of participants in the safety sample.

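### No planned final AE summary table separates events after the saline injection from events after vaccine, and the Fisher comparison of study arms sets three injections against two

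*Protocol*

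**What the plan says.** Protocol 14.4.1 gives the safety sample and the classification rule: "All participants who consent and undergo screening procedures. Participants will be analyzed according to the vaccine they actually received", whatever the randomized arm. The same paragraph defines treatment-emergent as "any adverse event that occurs on or after the first injection" and limits treatment-emergent summaries to people who received any injection, placebo or active. SAP section 4 repeats the definition ("Safety sample: All participants who consent and undergo screening procedures") and the same limit.

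SAP 8.2 then plans an overall AE table and tables by system organ class and preferred term. Treatment-emergent AEs are tabulated by treatment group, cohort and overall, and Fisher's exact test compares the study arms. Neither grouping term is defined for these tables, and none is laid out by injection. On denominators SAP 8.2 says: "Percentages will be based on the number of participants in the safety population". SAP 9.1 says the same of medications: "Percentages will be based on the number of participants in the safety sample".

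Placebo is separated in two other places. DSMB reviews receive "a listing of all reported AEs and SAEs by vaccine arm/placebo and population" (Protocol 13.8.2.1). Secondary endpoint 5 (SAP 7.3.4) compares the placebo dose with active dose 1 for 90-minute systemic allergic reactions in the HA/MCD population.

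**The concern.** The saline arm exists to show what follows an injection that contains no vaccine. The final AE tables do not use it that way. If the columns follow vaccine received, an AE after saline in a placebo-first participant is counted under a vaccine that the person had not yet been given. If they follow randomized arm, the placebo-first columns mix saline and vaccine events over a longer period and are then tested against arms with fewer injections. Anyone who received only saline has no vaccine-received group. Such people can exist: Protocol 4.2 discontinues a participant who becomes pregnant after placebo and before vaccination.

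At stake are the reported AE rates by vaccine and the one inferential AE comparison in the SAP.

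**Working it through.** **The plan's own figures first.** Participation under versions 1.0-4.0 (Protocol 3.1), from the dosing intervals plus 7 days of follow-up:
- Pfizer-BioNTech: 1 + 21 + 7 = 29 days; placebo first, 1 + 21 + 21 + 7 = 50.
- Moderna: 1 + 28 + 7 = 36 days; placebo first, 1 + 28 + 28 + 7 = 64.

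All four match. The placebo-first window is 50/29 = 1.72 or 64/36 = 1.78 times as long. Under versions 5.0-8.0 the ratios are 36/29 = 1.24 and 43/36 = 1.19.

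**Saline share within a vaccine-received group.** Allocation is 2:1 within each vaccine (2:2:1:1 overall), with two injections against three (SAP 6.2). Saline is 1/(2×2 + 1×3) = 1/7 = 14.3% of planned injections. The days before any vaccine are 21/(2×29 + 50) = 21/108 = 19% of arm-weighted observed days for Pfizer-BioNTech and 28/(2×36 + 64) = 28/136 = 21% for Moderna.

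**Reading 1: columns by vaccine received.** Let v be the risk of a given AE after each vaccine dose and s the risk after saline. Both are assumed, independent across injections, with all injections given.
- Vaccine only: A = 1 − (1 − v)²
- Placebo first: B = 1 − (1 − s)(1 − v)²
- Pooled 2:1: (2A + B)/3

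| s | v | A | B | Pooled | Relative excess over A |
|---|---|---|---|---|---|
| 2% | 2% | 3.96% | 5.88% | 4.60% | 16% |
| 5% | 5% | 9.75% | 14.26% | 11.25% | 15% |
| 20% | 20% | 36.0% | 48.8% | 40.3% | 12% |
| 1% | 2% | 3.96% | 4.92% | 4.28% | 8% |
| 0 | 2% | 3.96% | 3.96% | 3.96% | 0 |

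**Reading 2: columns by randomized arm.** The vaccine-only columns are now free of saline events, but the Fisher test compares A with B. As an illustration, take the 1700 participants planned per vaccine (Protocol 14.7), split 2:1 into 1133 and 567. With s = v, so that vaccine adds nothing to the risk of an injection, the two-sided Fisher test at 0.05 rejects with probability of about 40% at 2% per injection (3.96% against 5.88%), 77% at 5% and 96% at 10% (19.0% against 27.1%). The direction is always against the placebo-first arm. Smaller tables, such as one cohort alone, would reject less often.

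**Denominator.** If a share u of the safety sample was never injected, an overall percentage p prints as p(1 − u). The documents do not state u. For a true 20.0%, u = 1%, 5%, 10% or 20% gives 19.8%, 19.0%, 18.0% or 16.0%. Under the vaccine-received rule only overall columns are touched, because someone never injected belongs to no vaccine column.

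**The case against.** The strongest reply is that the systemic allergic reactions this trial is about are analysed in SAP section 7, not in the safety tables. SAP 7.2.1 counts reactions to active doses only, SAP 7.2.4 gives rates by active dose, and secondary endpoint 5 isolates saline. That is right. A reader might infer that no final analysis separates saline from vaccine, or that the primary and secondary estimates are contaminated. The documents support neither. But endpoint 5 covers only 90-minute systemic allergic reactions in HA/MCD and is skipped if there are no placebo reactions. It says nothing about other AEs or the comparison group.

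A reader might also infer that AE percentages in general have a wrong denominator. They do not: Protocol 14.4.1 and SAP 4 already confine treatment-emergent summaries to injected participants. Nor is the consented denominator wrong for every line of the overall table. AEs are collected from consent (Protocol 13.4.1), so an allergic reaction before injection is possible. What stands is that SAP 8.2 names the whole safety population without repeating the limit. Some people withdraw before any injection (Protocol 12.4: "withdrawn from the study prior to receipt of study treatment will not be followed after their last completed study visit"), but pre-screening before consent and randomization at the injection visit suggest that the share is low.

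The 16% can be challenged too. SAP 6.2 names four arms, and if those are the columns, the vaccine-only rates are not inflated; the Fisher comparison is then the problem. Saline may also carry less risk than vaccine, and the table shows that the excess falls to nil as s goes to zero. Finally, final listings sort by time of assessment, so timing is recoverable, but a listing of records gives no rates.

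**Conclusion.** The point holds for the SAP 8.2 AE tables, on either reading of the undefined grouping terms. By vaccine received, vaccine rates are inflated by 12% to 16% relative if risk is equal after every injection (2% to 20% assumed), by about 8% if saline has half of a 2% vaccine risk, and by nothing if saline has none. By arm, the Fisher comparison is biased against placebo-first participants by the additional injection alone, and its rejection rate reflects that exposure as well as any vaccine effect. The per-injection risks are assumptions, since the documents give none.

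The denominator mismatch between SAP 8.2 and SAP 4 is a secondary inconsistency, confined to overall columns and of unstated, possibly small, size.

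**What to change.** In SAP 8.2:
- Assign each treatment-emergent AE to the injection it follows (placebo, active dose 1 or active dose 2). Use the number who received that injection as denominator, over a common window such as the 7-day solicited period.
- Base the Fisher comparison on these like-for-like periods, not on whole-study arms. First injection against first injection (saline in the placebo-first arms, active dose 1 in the vaccine-only arms) keeps the randomization.
- Define treatment group for the safety tables, with a placebo-only category.
- State injected participants as the denominator for treatment-emergent summaries, and keep the consented sample for AEs before the first injection.

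In SAP 9.1, use injected participants for the prior, concomitant and after classes, which need dosing dates.

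The cost is SAP wording and extra table shells. No new data are needed, since AE timing and placebo status are already used for the DSMB listings.
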